#### 10.1.2.4 Reporting and Handling of Pregnancies

Not applicable.

#### 10.1.2.5 Periodic reporting of safety

An Annual Safety Report is submitted once a year to the local Ethics Committee via Sponsor-Investigator.

#### 10.1.3 **Follow up of (Serious) Adverse Events**

All AEs or SAEs that result in a subject withdrawal from the study will be followed up until a satisfactory resolution occurs, or until a non-study related causality is assigned (if the volunteer consents to this).

### 10.2 **Assessment, notification and reporting on the use of radiation sources**

Not applicable.

## 11. STATISTICAL METHODS

### 11.1 Hypothesis

*Null Hypothesis (H0):* Children receiving early MMR at 6 months of age (Group M.C. or M.M.) will have the same number of respiratory infections between 6 months and 9 months of age than children receiving the regular MMR at 9 months of age (Group C.M. or C.C.).

*Alternative hypothesis (H1):* Children receiving early MMR at 6 months of age (Group M.C. or M.M.) will have less respiratory infections between 6 months and 9 months of age compared with children receiving the regular MMR at 9 months of age (Group C.M. or C.C.).

### 11.2 Determination of Sample Size

The sample size calculation for the clinical outcome (500 participants) is based on the primary outcome of respiratory infections. Based on the data from a previous trial, we expect a rate of respiratory infection of 0.29 episodes per month (SD 0.32) between 6 and 9 months of age in the control groups (Group C.M. or C.C.). By randomising 500 participants, we will have an 80% power to detect a minimum of 30% reduction in this incidence with a 2-sided p-value of 0.05, assuming at least 85% completion rate of the 9 months questionnaire. The 500 participants will be randomised into 4 groups of similar size (see Section 6 and table 3 in Section 8.1): for the primary outcome analysis, the 250 children receiving early MMR at 6 months of age (Group M.C. or M.M.) will be compared with the 250 children receiving the regular MMR at 9 months of age (Group C.M. or C.C.).

		Timing of the 2 nd MMR		
		2 nd MMR 1m after the 12y DPT-PCV (Modified)	2 nd MMR concomitant to the 12y DPT-PCV (Current)	
Primary outcome comparing the timing of the 1 st MMR	1 st MMR at 6m (Modified)	Group M.M., n=125	Group M.C., n=125	N=250
	1 st MMR at 9m (Current)	Group C.M., n=125	Group C.C., n=125	N=250
		N=250	N=250	

Table 7. Participant allocation in 4 groups; for the primary outcome analysis, the Groups M.C. and M.M. will be compared with the Groups C.M. and C.C. C: current MMR schedule; DTP: diphtheria-tetanus-pertussis vaccine; m: month; M: Modified MMR schedule; PCV: pneumococcal conjugate vaccine.

The sample size calculation for the laboratory outcomes (100 participants) is more conservative as it depends on the success of the blood collection and of the laboratory processing for each of the time points. The use of paired samples (taken from the same infant at different ages) reduces the effect of inter-individual heterogeneity and provides greater statistical power with lower participant numbers.

Among the 500 participants enrolled, 100 participants consenting to blood collection (Part 2) will be randomised into 4 groups of similar size (table 2 in Section 6.1): for the laboratory outcome analysis, the 50 children receiving early MMR at 6 months of age (Group M.C. or M.M.) will be compared with the 50 children receiving the regular MMR at 9 months of age (Group C.M. or C.C.). Assuming that at least 60% of participants from Part 2 will provide a sufficient blood sample at each time point, which will then be processed without any problem, these 100 participants in total are required for Part 2, to ensure that a minimum of 30 participants per group of 1st MMR timing (30 in Group M.C. or M.M., and 30 in Group C.M. or C.C.) could be included in all analyses.

		Timing of the 2 nd MMR		
		2 nd MMR 1m after the 12y DPT-PCV (Modified)	2 nd MMR concomitant to the 12y DPT-PCV (Current)	
Primary outcome comparing the timing of the 1 st MMR	1 st MMR at 6m (Modified)	Group M.M., n=25	Group M.C., n=25	N=50
	1 st MMR at 9m (Current)	Group C.M., n=25	Group C.C., n=25	N=50
		N=50	N=50	

Table 8. Participant allocation in 4 groups; for the laboratory outcome analysis, the Groups M.C. and M.M. will be compared with the Groups C.M. and C.C. C: current MMR schedule; DTP: diphtheria-tetanus-pertussis vaccine; m: month; M: Modified MMR schedule; PCV: pneumococcal conjugate vaccine.

**Cytokine secretion & ICS studies:** with a minimum of 30 participants per group of 1st MMR timing (30 in Group M.C. or M.M., and 30 in Group C.M. or C.C.) who could be included in all analyses (minimum of 60 in total) we would have >80% power to detect a biologically significant 1.5-fold-change in cytokine responses at the 5% significance level, based on the variance of previous infant cytokine and ICS studies.

**Transcriptomic analysis:** a minimum of 20 participants per group of 1st MMR timing (20 in Group M.C. or M.M., and 20 in Group C.M. or C.C.; 40 participant in total) provides 80% power to detect a 1.25 fold-change in RNA expression counts for RNASeq.

**Epigenetic analyses:** a minimum of 20 participants per group of 1st MMR timing (20 in Group M.C. or M.M., and 20 in Group C.M. or C.C.; 40 participant in total) provides 80% power to detect a mean difference of 9% at p<0.05 and a difference of 30% at the genome wide level.

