## 7.3 Assignment to study groups

Once informed consent is signed, consent to blood tests at 6, 9 and 24 months of age will be sought, and will determine whether a child participates in Part 1 only, or both Part 1 and Part 2. For subjects consenting to blood tests, the baseline blood will be collected prior to randomisation. In the eventuality that the blood collection fails, the subject will be considered as not consenting to blood tests (participation to Part 1 only), given that the laboratory analysis in Part 2 cannot be made in the absence of a baseline blood sample.

As described in section 6.2.1, randomisation will be in 4 groups of similar size, using a web-based randomisation procedure, stratified by consent to blood tests (yes/no), in randomly permuted blocks of variable length (4 or 8), enabling to prevent predictability of intervention assignments. The randomisation lists will be generated prior to the initiation of the study by someone not involved in the study analysis and will be integrated into REDCap.

Subjects will be randomised at 6 months of age by an investigator (or designee) using the REDCap platform. Subjects will receive the two MMR vaccines according to their randomisation group (current schedule or modified schedule for the first and the second MMR dose, see section 6).

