### 9.3.2 Visit 1: Baseline and randomisation, 6 months of age ( $t_0 \pm 2$ weeks)

**Eligibility check** by investigators, with review of past medical history and of vaccination records, re-evaluation of inclusion and exclusion criteria.

**Target clinical examination** will be performed if needed, to ensure that there is no temporary exclusion criteria (e.g. if the child is sick, the inclusion can be delayed a few days until the illness resolves).

**Overview of the trial** by investigators, using the study flow chart and the participant informed consent form. Correct comprehension of the trial will be checked, with the possibility for parents to ask any remaining question.

**Blood collection will be discussed** in further details for interested parents.

**Further information** will be given to all parents, including that

- The treating physician of their child will be contacted to inform about the trial, corroborate their child's medical history and seek additional information.
- Authorised individuals other than their treating physician may examine their child's medical records.
- The blood samples taken as part of the study will be coded and stored for a period of maximum 15 years; this duration has been chosen given the likelihood that progress in the nascent field of non-specific effects of vaccines may benefit substantially from the reanalysis of study samples. Upon the approval of the Sponsor, samples may be sent outside of Switzerland to collaborating research laboratories for non-commercial research purposes.
- There is no compensation for participating in the trial.
- They are free to withdraw at any time. Unless they specifically request complete consent withdrawal, the long-term data collection, including access to medical records, will continue, in order to avoid bias as much as possible.

**Informed consent** will be sought, once the subject's parent confirm understanding and voluntarily agreeing in participating; the parent and the investigator will both date and sign the consent form.

**Inclusion in the trial**, the parent is given a copy of the signed document; the original copy is securely filed in the study documentation.

**Baseline questionnaire** will be filled down by the subject parents and reviewed with the investigator. It includes questions on demographics, medical history, and exposure, as detailed in Table 4 in section 9.2.

**Eczema assessment** will be performed, using *SCORAD* score.

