**Part 2 only: blood will be collected** (maximum 15 ml), in subjects whose parent accepted blood collection, for the laboratory tests listed in section 9.2.2. This is done after informed consent is obtained but prior to randomisation. In the eventuality that the blood collection fails, the subject will be considered as not consenting to blood tests (participation to Part 1 only), given that the laboratory analysis in Part 2 cannot be made in the absence of a baseline blood sample.

**Randomisation** in the trial, using a web-based randomisation procedure integrated into REDCap, stratified by consent to blood tests (yes/no), in randomly permuted blocks of variable length (4 or 8), enabling to prevent predictability of intervention assignments.

**Distribution of the vaccination plan** according to the group the subject has been randomised to.

**Group M.C. or M.M. only: MMR vaccination (first dose)**; Subjects randomised to the Group M.C. or M.M. (modified schedule for the 1st MMR dose) will receive one dose of MMR vaccine. After reconstitution of the vaccine by adding the entire content of the pre-filled syringe of solvent to the vial containing the powder, the vaccine (0.5 ml) will be injected intramuscularly in the deltoid region or in the anterolateral area of the thigh. The subject will be distracted during the injection, in order to minimise the pain. The subject will remain under close observation for 20 minutes after the injection.

**Group C.M. or C.C. only: No vaccination**; Subject randomised to the Group C.M. or C.C. (current schedule for the 1st MMR dose) will not receive any vaccine at 6 months.

**Vaccine diary** will be presented to the parents, who will be instructed to fill it for the next 42 days.

**Fortnightly questionnaire** will be presented to the parents, who will be instructed to fill them every 2 weeks for the next 18 months.

**Contact details** will be given to the parent, consisting in an emergency card with a phone number to call in case of questions about the trial or upon occurrence of any adverse event.

**Scheduling** next visits.

Once the subject and their parent have left:

**Data entry** will be checked by the investigator to ensure that no information is missing. Parents could be contacted if any data is missing.

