### 11.4.3 Secondary Analyses

The socio-demographic and clinical characteristics of the participants will be described using standard descriptive statistics (frequencies, medians and interquartile ranges, or means and standard deviation). Other comparative analyses at the 9-months and 2-years endpoints will be performed using chi-square test (or Fisher's test when appropriate) for categorical variables, and paired t-test or Wilcoxon signed-rank test for continuous variables, depending on the distribution of the variable. Time-to-event outcomes will be assessed using Cox proportional hazards with adjustment for baseline risk factors. Factorial analysis will enable to measure the effect on all outcomes of the intervention made to the first and the second dose of MMR, separately or in combination.

The infection outcomes of the 2-year endpoint will be analysed in two stages:

1) first we will examine the infection count distributions in the 4 experimental conditions: standard schedule (Group C.C.), early first dose (Group M.C.), separated 2nd dose (Group C.M.), both intervention (Group M.M.). We will check if the effects of one intervention appear similar across strata of the other intervention. This will be done to identify strong qualitative interactions (e.g., absence of effect in one stratum versus presence in the other), and to guide the regression models.

2) then we will use negative binomial regression models, starting with a model that includes an interaction term:

$\log(\text{infections}) = b_0 + b_1 \cdot \text{early} + b_2 \cdot \text{separate} + b_3 \cdot \text{early} \cdot \text{separate}$  where "early" and "separate" designate the 2 components of the intervention, both coded as 0 or 1. We will consider the coefficient  $b_3$  to decide on further analysis. If  $b_3$  is of small magnitude (in clinical and scientific terms) we will conclude to the absence of a statistical interaction (on a multiplicative risk scale), and we will drop the interaction term from further analysis. If  $b_3$  is of substantial size, further analysis will proceed as though the trial was a 4-arm trial, with 3 interventions (Group M.C, Group C.M. and Group M.M.) compared to the standard schedule arm (Group C.C.). The assessment of  $b_3$  will be based primarily on scientific and clinical relevance, not on statistical significance.

Model in absence of interaction:

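### The protocol counts on paired blood samples for power, but no named laboratory analysis brings the 6-month value into the comparison of the randomised groups

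*Protocol*

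**What the plan says.** **Baseline sample.** Protocol section 7.3 says: "For subjects consenting to blood tests, the baseline blood will be collected prior to randomisation". Section 9.3.2 agrees: "This is done after informed consent is obtained but prior to randomisation". Both sections move a child whose baseline draw fails to Part 1, on the ground that the Part 2 laboratory analysis is impossible without that sample.

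**Power argument.** Section 11.2 says: "The use of paired samples (taken from the same infant at different ages) reduces the effect of inter-individual heterogeneity", and that this allows fewer participants for the same power. The comparison is by timing of the first MMR dose: "for the laboratory outcome analysis, the 50 children receiving early MMR at 6 months of age" (groups M.C. and M.M.) against the 50 in groups C.M. and C.C. The evaluable number rests on this: "Assuming that at least 60% of participants from Part 2 will provide a sufficient blood sample at each time point", which leaves 30 per group. The claim for cytokine and ICS outcomes is ">80% power to detect a biologically significant 1.5-fold-change in cytokine responses at the 5% significance level". The variance is attributed to earlier infant studies; no SD or correlation is printed.

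**Named analyses.** Section 11.4.3 begins: "Other comparative analyses at the 9-months and 2-years endpoints will be performed using chi-square test". For continuous variables, the same sentence names the paired t-test or the Wilcoxon signed-rank test. The synopsis repeats this. Factorial analysis is promised for all outcomes. AIM9 (sections 5.2 and 9.2.2) adds multivariate analyses of the laboratory outcomes, listing the interventions, host factors, exposures, underlying immunity and family history. The child's own 6-month laboratory value is not listed.

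**The concern.** The power argument and the named tests do not fit together. A paired t-test or signed-rank test asks whether a child's value changed between two ages. It does not compare the children randomised to MMR at 6 months with those randomised to 9 months, who are independent samples. Replacing the paired tests with two-sample tests would give a valid randomised comparison, but the 6-month value would still go unused.

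At stake is the efficiency of the main laboratory contrast. With about 30 children per group, an analysis of follow-up values alone keeps all the between-child variation that the baseline sample could partly remove. It also leaves any chance baseline difference between the groups in the estimate. The protocol insists on collecting the one variable that addresses both problems, then names no analysis that uses it in the group contrast.

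**Working it through.** **Inputs from the protocol.** n = 30 per group (60% of 50); effect ln 1.5 = 0.405 on the log scale; power above 80% at the 5% level (section 11.2); two-sided tests (section 11.4).

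**Inputs the protocol does not give.** The SD of the log response, and the correlation ρ between the 6-month and follow-up values. The ρ values below are assumptions.

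**1. The plan's own figure.** It cannot be reproduced without an SD. Assuming an unadjusted two-group comparison, the SD that gives exactly 80% is

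SD = ln 1.5 / [(1.960 + 0.842) × √(2/30)] = 0.405 / (2.802 × 0.258) = 0.56

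(0.55 with the t distribution). The claim of more than 80% therefore needs a natural-log SD of about 0.56 or less. At SD 0.5 the power would be 88%; at SD 0.7 it would be 61%.

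**2. Adjusting for baseline (ANCOVA).** The residual SD is SD × √(1 − ρ²), so power = Φ(2.802/√(1 − ρ²) − 1.960) from an 80% base. At ρ = 0.5: 2.802/0.866 = 3.235; 3.235 − 1.960 = 1.275; Φ = 89.9%. The t-based calculation with 57 degrees of freedom agrees to within 0.1 point.

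**3. Change score, for contrast.** Its SD is SD × √(2(1 − ρ)).

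| ρ (assumed) | Follow-up only | ANCOVA | Change score |
|---|---|---|---|
| 0.2 | 80% | 81.6% | 60.1% |
| 0.3 | 80% | 83.6% | 65.8% |
| 0.5 | 80% | 89.9% | 80.0% |
| 0.7 | 80% | 97.5% | 95.1% |
| 0.8 | 80% | 99.7% | 99.3% |

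How the pairing is used therefore matters. A between-group test of change loses power below ρ = 0.5 and gains nothing at 0.5.

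**4. If unadjusted power is above 80%.** At ρ = 0.5, a base of 85% becomes 93.3% (+8.3 points) and a base of 90% becomes 96.3% (+6.3 points). The 9.9 points from an 80% base are thus about the most that ρ = 0.5 can give under the stated claim.

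**5. If the stated power already counts on baseline adjustment.** Suppose the adjusted analysis has exactly 80%. The unadjusted comparison then has Φ(2.802 × 0.866 − 1.960) = Φ(0.466) = 68% at ρ = 0.5.

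**6. In sample-size terms.** At ρ = 0.5, 30 × (1 − 0.25) = 22.5, so 23 per group with adjustment match 30 without it.

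**The case against.** The best case for the protocol is that this is silence rather than error. Section 11.4 gives the tests only in brief and leaves full details to a statistical analysis plan, which is not available here. The intention to use the baseline is plain: the sample is mandatory, section 11.2 invokes pairing, AIM7 compares gene expression between groups and between time points, and AIM8 compares vaccine responses with the pre-vaccination sample and between groups. The synopsis and AIM9 promise regression and multivariate models, with factors given as examples.

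Much of this stands, and it limits the point in four ways.

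- A reader might infer that the laboratory comparison will be unadjusted. No section says so; the protocol names no baseline-adjusted model, which is a narrower statement.
- A reader might quote a loss of 9 to 10 points as a fact. It depends on ρ = 0.5 and an unadjusted power of exactly 80%, neither of which is documented. Nor need ρ be the same at 9 and 24 months.
- A reader might call the baseline value complete by design. The rule secures a collected sample, not a usable assay; the 60% allowance covers sample sufficiency and processing at every time point.
- A reader might extend the point to SCORAD, which is also scored at Visit 1. The protocol lists it as a flare-severity score without a model, and the infants are healthy with severe eczema a ground for exclusion, so many zeros are plausible and a log-scale ANCOVA is not obviously workable.

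What the objection does not remove is that section 11.4.3 does name tests, and they are the wrong kind for the contrast defined in section 11.2. Nor does AIM8 supply the missing adjustment: its reference sample is taken at 6 or 9 months depending on the group, so for the 9-month groups it is post-randomisation.

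**Conclusion.** The point holds as a mismatch inside the protocol. Power is claimed from paired samples, but the named tests for continuous outcomes do not compare the randomised first-dose groups, and no named laboratory analysis carries the 6-month value into that comparison.

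The size is conditional. From an unadjusted 80%, ANCOVA adds about 2 points at ρ = 0.2, 4 at 0.3, 10 at 0.5 and 17.5 at 0.7, and less from a higher base. If the stated power already relies on adjustment, the risk runs the other way: an unadjusted analysis would fall short of the claim, at about 68% for ρ = 0.5. The protocol does not show which reading applies.

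This concerns the efficiency of secondary laboratory outcomes. The primary outcome is unaffected, and a two-sample comparison without baseline would still be valid. The change is worth making because the data are already being collected.

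**What to change.** In section 11.4.3 and the synopsis, state that continuous laboratory outcomes such as cytokine responses are compared between first-dose groups (M.C. and M.M. v C.M. and C.C.) by ANCOVA on the log scale. The log 9-month or 24-month value is the outcome and the log 6-month pre-randomisation value is the covariate. Report an adjusted geometric mean ratio with 95% confidence interval. Keep the paired tests, if wanted, only as descriptions of within-child change.

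In section 11.2, give the SD and the baseline-to-follow-up correlation behind the power claim, and say whether the claim already counts on adjustment.

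The adjusted model applies to Part 2 children. Part 1 children who give only the optional 24-month sample under AIM8 have no 6-month value, so say how they enter that comparison.

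The cost is wording and one degree of freedom, with no new visits, samples or assays. The possible gain should not be used to reduce Part 2, because the correlation is not known.

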### 11.3 Statistical criteria of termination of trial

Not applicable.

### 11.4 Planned Analyses

The full details of the analysis will be provided in the statistical analysis plan, which will be finalised prior to database lock. Briefly, all tests will be 2-tailed and a P<.05 will be considered statistically significant for the primary outcome. Non-parametric tests will be used when variables are not normally distributed.

#### 11.4.1 Datasets to be analysed, analysis populations

The groups will be compared by intention-to-treat analysis. Sensitivity analysis will be done using an as-treated (per-protocol) analysis and will only include participants with available data who received the interventions as planned.

Subgroup analysis are planned (by sex, risk factor, underlying maternal immunity, etc.) and will be detailed in the statistical analysis plan.

#### 11.4.2 Primary Analysis

This will be a classic 2-arm trial with regard to the first intervention (early 1st dose of MMR) and the primary outcome (number of respiratory infections between 6 and 9 months of age). The analysis of the

primary outcome will be performed by means of a regression model (either logistic, if the primary outcome is dichotomised as 0 vs  $\geq 1$ , or negative binomial, if numbers of infection episodes are left uncategorized) and will compare the two group of 1st MMR timing (Group M.C. or M.M. vs. Group C.M. or C.C.). The model will be adjusted for sex (male/female), day-care attendance (yes/no), presence of comorbidities (yes/no), older siblings (yes/no), and will be presented as adjusted odd ratios, hazard ratio, or incidence rate ratios (aIRRs) with 95% confidence interval, according to the model chosen.

It will be done in collaboration with the Clinical Research Center at Geneva University Hospitals, once all participants have attended the 9 months visit.

